An AE requiring specific monitoring is a serious or nonserious AE of scientific and medical concern specific to the Sponsor's product or program, for which ongoing monitoring may be appropriate. Such events may require further investigation to characterize and understand them. These events should be reported on the AE page and additional information required on the specific eCRF page (where applicable) and will only qualify for expedited reporting when serious (fulfilling SAE criteria).

The AEs requiring specific monitoring for this study are as follows:

- Severe GI events
- Severe hypoglycemia (see [Section 8.2.5](#))
- Pancreatic events (including abnormal values of pancreatic enzymes [see Appendix 7, [Section 10.5.2](#)]) – will be adjudicated by CEC
- Major adverse cardiovascular events (MACE; CV death, myocardial infarction, stroke) and other specific CV events (eg, heart failure leading to hospitalization) – will be adjudicated by CEC
- Calcitonin increase >5.9 pmol/L (20 pg/mL) and thyroid C-cell neoplasm (see Appendix 7, [[Section 10.5.3](#)])
- Acute renal failure (see Appendix 5 [[Section 10.5](#)] for definition)
- Diabetic retinopathy complications (will be reviewed by an independent ophthalmologist expert; see Appendix 1 [[Section 10.1.4.3](#)]); a written report from professional eye care provider will be required
- Severe injection site reaction
- Severe allergic reactions
- Severe immune complex disease

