#### **2.1.4.1 Adverse events observation period**

The AE observations will be classified per the observation periods of safety data as defined above into the following:

- **Pretreatment AEs** are AEs that developed or worsened or became serious during the pretreatment period
- **Treatment-emergent AEs (TEAEs)** are AEs that developed or worsened or became serious during the on-treatment period
- **Posttreatment AEs** are AEs that developed or worsened or became serious during the posttreatment period

All AEs (including serious adverse events (SAE), AESIs, and AEs requiring specific monitoring) will be coded to a lower-level term (LLT), preferred term (PT), high-level term (HLT), high-level

group term (HLGT), and associated primary system organ class (SOC) using the version of MedDRA currently in effect at the time of database lock.

Adverse events of special interest (AESI) include the following terms:

- Pregnancy of a female participant entered in a study as well as pregnancy occurring in a female partner of a male participant entered in a study with IMP/NIMP
- Symptomatic overdose (serious or non-serious) with IMP/NIMP
- Increase in alanine aminotransferase (ALT) >3 x upper limit normal (ULN)

Adverse events requiring specific monitoring (AERSM) include the following terms:

- Severe gastrointestinal (GI) events
- Severe hypoglycemia
- Pancreatic events (including abnormal values of pancreatic enzymes, pancreatitis and pancreatic neoplasm)
- Selected cardiovascular events (CV death, MI, stroke, heart failure leading to hospitalization, unstable angina, and transient ischemic attack [TIA])
- Calcitonin increase >5.9 pmol/L (20 pg/mL) and thyroid C-cell neoplasm
- Acute renal failure
- Diabetic retinopathy complications
- Severe injection site reaction
- Severe allergic reactions
- Severe immune complex disease

Independent Clinical Endpoint Committee(s) (CEC) will review, assess, and/or adjudicate all events of death, selected CV events and pancreatic events.

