### *General common rules*

All safety analyses will be performed on the safety population as defined in [Section 2.3.2](#), unless otherwise specified, using the following common rules:

- Safety data in participants who do not belong to the safety population (eg, treated but not randomized) will be listed separately
- The potentially clinically significant abnormality (PCSA) values are defined as abnormal values considered medically important by the Sponsor according to predefined criteria/thresholds based on literature review and defined by the Sponsor for clinical

laboratory tests, vital signs, and ECG (PCSA version 3 date dated 21May2014 effective date 24May2014 [[Appendix A](#)])

- PCSA criteria will determine which participants had at least 1 PCSA during the on-treatment period, taking into account all evaluations performed during the on-treatment period, including nonscheduled or repeated evaluations. The number of all such participants will be the numerator for the on-treatment period PCSA percentage.
- The treatment-emergent PCSA denominator by group for a given parameter will be based on the number of participants assessed for that given parameter in the on-treatment period and by treatment group on the safety population.
- The analysis of the safety variables will be descriptive, and no systematic testing is planned.

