### ***Analysis of all treatment-emergent adverse events***

The following TEAE summaries will be generated for the safety population.

- Overview of TEAEs, summarizing number (%) of participants with any
  - TEAE
  - Serious TEAE
  - TEAE leading to death
  - TEAE leading to permanent treatment discontinuation
  - Discontinued per investigator decision

- Discontinued per participant decision
- Treatment-related TEAE
- TEAEs of special interest (AESI)
- TEAEs requiring specific monitoring (AERSM)
- All TEAE by primary SOC, HLGT, HLT, and PT, showing number (%) of participants with at least 1 TEAE sorted by the SOC internationally agreed order. The other levels (HLGT, HLT, and PT) will be presented in alphabetical order. This sorting order will be applied to all other tables by SOC, HLGT, HLT, and PT, unless otherwise specified.
- Summary of common TEAEs (eg, PTs with incidence  $\geq 2\%$  in any treatment group) will be presented by primary SOC and PT.

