***Analysis of adverse events of special interest (AESI) and requiring specific monitoring (AERSM)***

TEAEs of special interest (AESI) and requiring specific monitoring (AERSM) include AE defined in [Section 2.1.4](#) and the criteria of AESI and AERSM are in [Table 1](#).

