**Table 1 - Criteria for AESI and AERSM**

AE Grouping	Criteria
AESI	
Pregnancy	"Pregnancy" or "Partner pregnancy" checked
Symptomatic Overdose	"Overdose" checked" and symptomatic (AEOVSYP) ="Yes"
Increase in ALT >3ULN	"ALT Increase" checked and Yes to the question "Is the event an AESI?" in eCRF form "Adverse Events"
AERSM	
Severe GI events	AE severity= "severe" using Gastrointestinal disorders CMQ
Severe hypoglycemia	Any hypoglycemia event which required assistance (from hypoglycemia page)
Pancreatic events	Cases reported in eCRF "Suspected or confirmed Pancreatitis" page or AE category = "Pancreatic Neoplasm"

AE Grouping	Criteria
Selected cardiovascular event	
Cases reported in the following specific eCRF pages:
 
 
• “Suspected or confirmed MI/Unstable Angina”
 
• “Suspected or confirmed cerebrovascular event”
 
• “Suspected or confirmed heart failure” led to unplanned hospitalization, led to urgent/unscheduled visit to emergency room or an urgent/unscheduled outpatient heart failure treatment unit, or infusion center, or office/practice visit, not followed by hospitalization, or occurred while patient was hospitalized for another reason
 
• Primary cause of death in eCRF “Death (CV)” as Acute MI, Sudden cardiac death, Heart failure or cardiogenic shock, Stroke, Complication of cardiovascular procedure, Other cardiovascular cause, or Undetermined cause of death
 

Calcitonin and thyroid C-cell neoplasm	
Using Calcitonin increase CMQ
 
Using Medullary thyroid cancer CMQ

Acute renal failure	Using Acute renal failure CMQ
Severe injection site reaction	Intensity = "Severe" + Using Injection site reaction_ CMQ.
Severe allergic reactions	Intensity = "Severe" + CMQs for anaphylactic reaction, angioedema, severe cutaneous adverse reaction, anaphylactic/anaphylactoid shock conditions (under SMQ "Shock"), and hypersensitivity.
Severe immune complex disease	Intensity = "Severe" using Immune complex disease CMQ
Diabetic retinopathy complications	Cases reported in eCRF “Diabetic Retinopathy Complementary Form”

The following TEAE summaries will be generated for the safety population:

- All AESI by prespecified grouping and PT, showing number (%) of participants with at least 1 AESI, with PTs sorted by decreasing order in Efpeglenatide 6 mg group

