- All AERSM by prespecified grouping and PT, showing number (%) of participants with at least 1 AERSM, with PTs sorted by decreasing order in Efpeglenatide 6 mg group.

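### Does SAP Table 1 count heart failure that the SAP's own description of the cardiovascular events leaves out?

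*SAP*

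**What the plan says.** Three parts of the SAP bear on the point.

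- Section 2.1.4.1 lists the AERSM. The cardiovascular entry reads "Selected cardiovascular events (CV death, MI, stroke, heart failure leading to hospitalization, unstable angina, and transient ischemic attack [TIA", and heart failure is the only one of its six components with a hospitalization condition.
- The AESI and AERSM paragraph in 2.4.4.1 ties that list to Table 1. It says "TEAEs of special interest (AESI) and requiring specific monitoring (AERSM) include AE defined in" Section 2.1.4, and then that "the criteria of AESI and AERSM are in" Table 1.
- The cardiovascular row of Table 1 takes cases from the heart-failure eCRF page if the event led to an unplanned admission, or to an urgent visit to an emergency room, outpatient unit, infusion center "or office/practice visit, not followed by hospitalization, or occurred while patient was hospitalized for another reason".

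The row feeds two displays: the line "TEAEs requiring specific monitoring (AERSM") in the overview of treatment-emergent events, and the table described as "All AERSM by prespecified grouping and PT, showing number (%) of participants with at least 1 AERSM". Under the common rules of SAP 2.4.4, "The analysis of the safety variables will be descriptive, and no systematic testing is planned".

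The protocol is looser than SAP 2.1.4.1. Section 8.3 lists major cardiovascular events and "other specific CV events (eg, heart failure leading to hospitalization"), where the abbreviation for an example leaves the list open.

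**The concern.** A description and its selection rule ought to pick out the same events, and the SAP links these two in one sentence. On heart failure they differ. A case handled at an urgent visit without admission is the opposite of heart failure that leads to admission, yet Table 1 counts it. If the two texts competed, two programmers could produce different cardiovascular counts per arm. A reader of the report who relied on 2.1.4.1 would also take the row to mean admitted heart failure only.

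This deserves a check because safety is a stated focus of the simplified SAP (section 2.4), and events requiring specific monitoring are among its main displays. The same label also appears in the adjudication text, so a reader might assume that everything in the row falls within the named remit of the Clinical Endpoint Committee (CEC).

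**Working it through.** The documents state no figure to reproduce, and the question turns on no sample size, power or alpha. The check compares texts, followed by one line of arithmetic on scale.

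**Step 1. Compare each Table 1 route with the 2.1.4.1 wording.**

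| Heart-failure route in Table 1 | Did heart failure lead to an admission? | Within 2.1.4.1? |
|---|---|---|
| (a) unplanned admission | Yes | Yes |
| (b) urgent visit, no admission afterwards | No | No |
| (c) onset during a stay for another reason | It did not cause the stay, but may have prolonged it | Arguable |

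Route (c) is arguable because the definition of a serious event in Protocol 10.3 treats prolonging an existing stay and being admitted as one criterion. So one route of three is clearly outside the description and one is open to argument. The phrase about no later hospitalization cannot be read as an exclusion, since it qualifies visits that are themselves listed as qualifying.

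**Step 2. Ask which text decides the count.** SAP 2.4.4.1 calls Table 1 the criteria. Table 1 names eCRF pages, fields and outcomes that can be programmed; 2.1.4.1 gives event names and no selection rule. The rest of the cardiovascular row behaves in the same way. It takes suspected as well as confirmed infarction or unstable angina, suspected as well as confirmed cerebrovascular events, and deaths of undetermined cause. Each is wider than its name in 2.1.4.1. Heart failure is therefore no isolated contradiction: 2.1.4.1 gives short labels and Table 1 gives the case definition.

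**Step 3. Check Table 1 against the protocol.** Protocol 8.3 gives admitted heart failure as an example only, so the wider row departs from nothing in its list of monitored events. The narrow wording is the SAP's own.

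**Step 4. Compare the output before and after aligning the texts.** Before: the row counts routes (a), (b) and (c). After rewording 2.1.4.1 to match Table 1: it still counts (a), (b) and (c). Change in any participant's classification: 0. Change in any count: 0.

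**Step 5. Put a scale on the row.** A participant who enters only through (b) or (c) adds 1/n to the arm's percentage.

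- Planned n = 160: 1/160 = 0.625%, about 0.6 percentage points.
- Assumed n = 80: 1/80 = 1.25%.
- Assumed n = 40: 1/40 = 2.5%.

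The values 80 and 40 are assumptions, because the documents do not give the number randomized at early termination. These figures show what one participant contributes. They are not evidence that anyone entered by these routes.

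**The case for a change.** The strongest reply is that if Table 1 governs, 2.1.4.1 is wrong as written and should be corrected. The hospitalization condition there has no function if other heart failure also counts, and the wording carries no sign of being an example. A reader could misread the row, and a separate line for admitted heart failure would prevent that at little cost.

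Part of this stands: the wording of 2.1.4.1 is narrower than the row, and a careful reader will notice. Three things limit what follows.

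- The separate line is a matter of presentation. Table 1 already includes every route, so no case is lost without it. A treatment-emergent heart-failure event that led to inpatient admission is serious under Protocol 10.3 and so appears by preferred term in the serious-event table. The listing of events sent for adjudication also shows seriousness criteria.
- Rewording 2.1.4.1 is not quite free. Its closing sentence sends selected cardiovascular events to the CEC, while the adjudication paragraph of SAP 2.4.4.1 and Protocol 10.1.4.2 name only admitted heart failure, plus other events set by the charter. Widening the label alone would move the mismatch into the CEC remit.
- Misreading is a reporting matter. Whoever writes the synopsis report will describe the row by the criteria that produced it.

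A related question is whether the pancreatic row omits isolated enzyme elevations, which 2.1.4.1 includes. The documents do not show that it does. Protocol 10.5.2.2 sends confirmed isolated elevations, suspected pancreatitis and confirmed pancreatitis to the same kinds of form, differing in the reported term. Whether those forms include the page named in Table 1 depends on an eCRF layout that cannot be seen here.

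**Conclusion.** The inconsistency is real, but it is editorial. SAP 2.1.4.1 uses a shorter label than the rule in Table 1; Table 1 supplies the criteria and is compatible with Protocol 8.3. Analysts have one workable rule, and aligning the wording would change no classification, count or percentage. What is affected is the reading of one descriptive row, in a simplified SAP with no safety testing.

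The conclusion assumes that Table 1 was programmed as written, which is the natural reading of SAP 2.4.4.1. The number of participants entering by the two additional routes cannot be known from the documents. Whatever it is, it is the same under the current text and under a corrected label, so no change to the plan follows.

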### ***Analysis of adjudicated events***

All events of death, selected cardiovascular events (MI, stroke, unstable angina leading to hospitalization, and heart failure leading to hospitalization), any pancreas-related events, and other selected AEs (as defined in the CEC charter) will be reviewed, assessed, and/or adjudicated by CEC. The events sent for adjudication will be presented in the listings, which will include at least the following information, sorted by treatment, participant identification, and onset date: treatment, participant identification, country, age, gender, race, primary SOC, PT, reported term, onset date, study day (relative day to the start date of IMP), AE duration, duration of exposure, intensity, action taken with IMP, date of treatment discontinuation (if relevant), relationship to

IMP/NIMP/study procedures, outcome, date of death (if any), seriousness, seriousness criteria, and AE status (“Pre” for a pretreatment AE; “T” for a TEAE; and “Post” for a posttreatment AE).

#### **2.4.4.2 Analysis of hypoglycemia**

Treatment-emergent hypoglycemia events will be tabulated separately from the AEs.

Event frequency and incidence of hypoglycemia events will be summarized by treatment for all reported hypoglycemia and per type of hypoglycemic event described in [Section 2.1.4.6](#) (ie, severe, documented symptomatic, asymptomatic, probable symptomatic, relative). Documented hypoglycemia (symptomatic or asymptomatic) will be also evaluated for the more stringent plasma glucose threshold of 3.0 mmol/L (<54 mg/dL), as well as for  $\geq 3.0$  and <3.9 mmol/L ( $\geq 54$  and <70 mg/dL), and  $\leq 3.9$  mmol/L ( $\leq 70$  mg/dL). Frequency and percentage of participants with at least 1 hypoglycemia event will be summarized as well.

Event rate of hypoglycemia per participant year will be calculated by treatment using the total number of hypoglycemia events from all participants (denoted as n) divided by the total exposures from all participants expressed in years (ie, participant exposure in days divided by 365.25, denoted as t). Multiple events from an individual participant will all count. Event rates of hypoglycemia per participant year (all reported hypoglycemia, severe, documented symptomatic, asymptomatic, probable symptomatic, relative hypoglycemia, and documented hypoglycemia with plasma glucose <3.0 mmol/L [ $< 54$  mg/dL], as well as for  $\geq 3.0$  and <3.9 mmol/L [ $\geq 54$  and <70 mg/dL], and  $\leq 3.9$  mmol/L [ $\leq 70$  mg/dL]) will be presented by treatment group for the on-treatment period.

A listing of participants for all severe hypoglycemia events reported on the specific eCRF “Hypoglycemic Event Information” page will be provided.

#### **2.4.4.3 Deaths**

A listing of all deaths for screened participants will be generated.

#### **2.4.4.4 Analyses of vital sign variables**

The incidence of PCSAs at any time during the on-treatment period will be summarized for heart rate by treatment group irrespective of the Baseline level and/or according to the following Baseline status categories:

- Normal/missing
- Abnormal according to PCSA criterion or criteria

## 2.5 DATA HANDLING CONVENTIONS

### 2.5.1 General conventions

The following formulas will be used for computation of parameters.

#### *Demographic formulas*

The participant's duration of diabetes (years) is calculated using the date of informed consent and the date of diabetes diagnosis.

If date of diabetes diagnosis is a complete date, then the duration of diabetes is (date of informed consent - date of diabetes diagnosis + 1) / 365.25. If date of diabetes diagnosis is a partial date, then the duration will be calculated using the following:

- A) year and month are not missing, but day is missing, then day = 01
- B) year is not missing, but month and date are both missing, then month is imputed to January and the day = 01.

#### *Renal function formulas*

eGFR will be calculated using the 4-variable Modification of Diet in Renal Disease (MDRD-4) formula below(1):

- $eGFR \text{ (mL/min/1.73 m}^2\text{)} = 175 \times \text{serum creatinine (mg/dL)}^{-1.154} \times \text{Age(year)}^{-0.203} \times 1.212 \text{ [if black]} \times 0.742 \text{ [if female]}$

### 2.5.2 Data handling conventions for secondary efficacy variables

No special data handling conventions will be used.

### 2.5.3 Missing data

For categorical variables, participants with missing data are not included in calculations of percentages unless otherwise specified. When relevant, the number of participants with missing data is presented.

Derived variables will be considered missing if any of the original variables required to calculate them are missing. For example, if either a baseline assessment or an endpoint assessment is missing for a particular participant, then change from baseline at endpoint will be missing. Depending upon the assessment, analyses may not include all participants in the analysis population, because certain participants in the intended population may have missing data.

***Handling of computation of treatment duration if investigational medicinal product end of treatment date is missing***

For the calculation of the treatment duration, the date of the last dose of IMP is equal to the date of last administration reported on the treatment status case report form page. If this date is missing, the exposure duration should be left as missing.

In the definition of the on-treatment period, the date of the last dose of IMP is equal to the date of the last administration reported on the treatment status case report form page. If this date is missing, the date of the last IMP injection in the exposure page will be used for participants with at least 1 injection or the date of visit 2/randomization visit will be used for participants who were lost to follow-up after the initial dispensation of IMP.

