#### ***Observation period***

The observation period will be divided into 3 main segments:

- The **pretreatment** period is defined as the time from informed consent up to the time of first injection of IMP
- The **on-treatment** period is defined as the time from the first injection of the IMP up to 30 days (7 days for hypoglycemia) after the last injection of the IMP
- The **posttreatment** period is defined as the period from the end of the whole on-treatment period

The **on-study observation** period is defined as the time from first injection of IMP up to either the last protocol-planned visit or the date of last available information if participants discontinue the study prematurely (ie, the date collected on e-CRF page “Completion of End of Study/Follow-up”), whichever is later.

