***Handling of adverse events/hypoglycemia with missing or partial date/time of onset***

Missing or partial AE/hypoglycemia onset dates and times will be imputed so that if the partial AE/hypoglycemia onset date/time information does not indicate that the AE/hypoglycemia started prior to treatment or after the on-treatment period, the AE/hypoglycemia will be classified as treatment-emergent. No imputation of AE end dates/times will be performed. These data imputations are for categorization purpose only and will not be used in listings. No imputation is planned for date/time of AE resolution.

***Handling of adverse events/hypoglycemia when date and time of first investigational medicinal product administration is missing***

When the date and time of the first IMP administration is missing, all AEs/hypoglycemia that occurred on or after the day of randomization should be considered as TEAEs. The exposure duration should be kept as missing.

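### When a first- or last-dose date is missing, the SAP can count hypoglycemia events in the per-participant-year rate without the matching person-time

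*SAP*

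**What the plan says.** **Complete dates.** SAP 2.1.4 (Observation period) runs the on-treatment period from the first injection "up to 30 days (7 days for hypoglycemia) after the last injection of the IMP". SAP 2.4.2.1 defines exposure as last dose date minus first dose date plus 7 days. For hypoglycemia, the event window and the person-time therefore cover the same days.

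**The rate.** SAP 2.4.4.2 computes it for the on-treatment period, by treatment. The numerator is formed "using the total number of hypoglycemia events from all participants". That count is then "divided by the total exposures from all participants expressed in years".

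**Last-dose date missing on the treatment status page (SAP 2.5.3).** For exposure: "If this date is missing, the exposure duration should be left as missing". The on-treatment period is closed in one of two ways. Where injections are on record, "the date of the last IMP injection in the exposure page will be used for participants with at least 1 injection". Where the participant did not come back after receiving the first kit, a visit date serves instead: "the date of visit 2/randomization visit will be used for participants who were lost to follow-up after the initial dispensation of IMP".

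**First-dose date missing (SAP 2.5.3).** For events: "all AEs/hypoglycemia that occurred on or after the day of randomization should be considered as TEAEs". For exposure: "The exposure duration should be kept as missing".

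**Who stays in.** Under SAP 2.3.2, a participant who was dispensed study drug and then lost without documented evidence of not taking it is treated as exposed and remains in the safety population.

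**The concern.** Each missing-date rule gives one answer for the numerator and another for the denominator. An affected participant can have countable hypoglycemia events and no exposure. The rate formula sums each side separately, so those events are divided by other participants' time.

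Hypoglycemic events per participant-year is a secondary safety endpoint in Protocol Table 1, and safety is among the analyses that SAP 2.4 keeps after early termination. Two programmers could also follow the SAP in good faith and report different rates. One would keep these participants' events and the other would drop them.

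**Working it through.** The documents state no hypoglycemia rate, event count or number of missing dose dates, so there is no figure of the plan's to reproduce. The check sets the rules side by side and then sizes the effect under stated assumptions.

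**Step 1. The rules by case**

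| Case | Event window for hypoglycemia | Person-time |
|---|---|---|
| Both dates known | First injection to last injection + 7 days | Last − first + 7 days |
| Treatment-status last-dose date missing, injections on exposure page | Closed from exposure-page last injection | Missing |
| Lost after initial dispensation | Closed from visit-date fallback | Missing |
| First-dose date missing | All events from randomization, no end stated | Missing |

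Only the first row matches.

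**Step 2. Does another rule repair it?** The opening of SAP 2.5.3 makes a derived variable missing when any of its inputs is missing. That makes the participant's exposure missing. An event count does not use the exposure value, so the events remain. The same section says analyses may not include every participant, but this is permissive and removes no events.

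**Step 3. Size.** Let m be the affected participants in an arm, e the weeks of window omitted for each, N the arm size and E the mean exposure in weeks of the others. If affected participants have events at the same rate as the rest of the arm,

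relative overstatement = omitted / counted person-time = m·e / ((N − m)·E).

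N = 160 is the planned arm size (SAP 1.1). E = 30 is the planned treatment period, and E = 15 is an assumed value for shortening by early termination. The values of m and e are assumptions.

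*Exposure-page fallback, e = 4:*

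| m | E = 30 | E = 15 |
|---|---|---|
| 0 | 0 | 0 |
| 4 | 16/4680 = 0.34% | 16/2340 = 0.68% |
| 8 | 32/4560 = 0.70% | 32/2280 = 1.40% |
| 16 | 64/4320 = 1.48% | 64/2160 = 2.96% |

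*Randomization-date fallback, 7 days omitted, e = 1:* from 2/4740 = 0.04% (m = 2) to 16/4320 = 0.37% (m = 16) at E = 30, and from 2/2370 = 0.08% to 16/2160 = 0.74% at E = 15.

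**Step 4. If affected participants have no counted events.** The rate as written then equals the rate with those participants left out of both sides. No event has entered without person-time, so the step 3 percentages do not measure a mismatch in that case.

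**Step 5. The visit label.** The schedule places randomization at Visit 3, and Visit 3 falls 4 to 10 days after Visit 2. Closing the window 7 days after Visit 3 gives 7 days from randomization. Closing it 7 days after Visit 2 puts the end between 7 − 10 = −3 and 7 − 4 = +3 days from randomization. The label therefore affects both the event window and any person-time taken from it.

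**The case against.** **The general missing-data rule could cover this.** One can read SAP 2.5.3 so that a participant with missing exposure contributes to neither side. That reading is possible, but the text does not state it for a group-level rate.

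**Two of the three routes are nearly empty.** Dose 1 is given on site at Visit 3 and Protocol Table 2 requires every injection date to be recorded, so a missing first-dose date should be rare. A participant lost after the first dispensation is unlikely to return the diary in which hypoglycemia is documented, so few events can enter that way. Both points stand. The main route is a blank treatment-status date beside a completed exposure page.

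**Counting doubtful events is conservative.** SAP 2.4.4.1 takes that stance for classifying adverse event onset, and it is reasonable for deciding whether an event is treatment-emergent. It does not justify omitting person-time. The rules also apply to placebo, where an inflated rate would favor the active arms.

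**The rate is descriptive.** SAP 2.4.4 plans no systematic testing, and this is a simplified SAP for a synopsis report. This stands and limits the consequence.

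**A stronger reading.** A reader might infer that the reported rates will be materially inflated or that the comparison with placebo is distorted. If 16 of 160 participants each lost a full 30 weeks of person-time, the formula gives 480/4320 = 11.1%. The documents do not support this. They give no count of missing dates, overall or by arm, and that scenario needs long treatment with no recorded last-dose date in a tenth of an arm.

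**Conclusion.** The mismatch is in the stated rules, and no other rule in the SAP resolves it. Hypoglycemia events can enter the rate without person-time when a first- or last-dose date is missing. Relative to a matched rate, the bias is upward only where affected participants have counted events.

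Its size is unknown. It is nil with no missing dates, and about 0.3% to 3% if 4 to 16 of 160 participants are affected, 4 weeks are omitted for each, event rates are equal and the others average 30 or 15 weeks. At the top of that range, 1.00 event per participant-year would be reported as 1.03.

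The net error against the true rate need not be upward, because a fallback date earlier than the true last dose can also drop events. The number of participants with at least one event is unaffected. The correction is worth making because it is cheap and makes the rate reproducible; the case does not rest on a large effect.

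**What to change.** For the hypoglycemia rate only:

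1. Compute person-time from the same start and end dates that define the event window, including the fallbacks already in SAP 2.5.3. These are the exposure-page last injection, the randomization visit for those lost after initial dispensation, and randomization as the start when the first-dose date is missing. End events and person-time 7 days after the last-dose date so obtained.
2. State that, for the rate, this also closes the event window for participants with a missing first-dose date. This narrows the current rule. All their events from randomization stay treatment-emergent in the incidence counts and listings.
3. If no window can be established, leave the participant out of both numerator and denominator of the rate, and report the number affected per arm.
4. Reconcile the visit label in "the date of visit 2/randomization visit will be used for participants who were lost to follow-up after the initial dispensation of IMP" with the schedule, where randomization is Visit 3.

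The cost is a few sentences in SAP 2.5.3 and 2.4.4.2 and a minor programming change, with no new data. The rate denominator may then differ slightly from the cumulative exposure reported under SAP 2.4.2.1, so the table needs a footnote. For participants lost after dispensation, the fix also credits up to 7 days in which events were probably not ascertained. By the step 3 figures this is a small effect.
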